3.2.3 Primary Safety Endpoints

Study follow-up will be conducted monthly, over a 6-month period upon completion of the study in order to determine the duration and stability of clinical improvements. In addition, a clinical assessment will be conducted at the end of each 2-week administration of TMS to any changes in mood and/or symptoms across the study as it is completed.

4 Study Population and Duration of Participation

We plan to enroll 80 patients to obtain useable data from 40 patients diagnosed with PTSD or trauma induced MDD and symptoms of depression, as determined by meeting the DSM criteria for PTSD or trauma induced MDD and having a PHQ-9 score \geq 10, will be recruited for this study. Participants will be otherwise healthy, aged 18-60, without significant concomitant diagnoses.

4.1 Inclusion Criteria

- 1. 18-60, male or female, any race
- 2. DSM-5 Diagnosis of PTSD or trauma induced MDD
- 3. PHQ-9 Score ≥10
- 4. Capacity to give informed consent and follow study procedures
- 5. English speaking

4.2 Exclusion Criteria

- 1. Significant handicaps (e.g. intellectual disability) that would interfere with testing procedures
- 2. MRI contraindications (e.g. foreign metallic implants, pacemaker, shrapnel or other metal in/on the body that cannot be removed, claustrophobia, etc.)
- 3. Additional TMS counter-indications (seizure disorder, CNS active disorder, certain medications described below)
- Medication use that substantially reduces seizure threshold to TMS (olanzapine, chlorpromazine, lithium) and unwilling or unable medically to safely withdraw, at least two weeks prior to TMS, from these medications
- 5. Previous unsuccessful treatment with full trial of TMS, ECT, or deep brain stimulation (DBS).
- 6. Opiate medication
- 7. Known neurological disorders including multiple sclerosis, encephalopathy, seizure disorder, brain tumors
- 8. Current problematic alcohol or substance abuse disorder, bipolar disorder (as PI discretion), schizophrenia or other psychotic disorder.
- 9. Refusal to agree to abstain from illicit drug use for duration of the study
- 10. Refusal to agree to abstain from alcohol within 24 hours of scans
- 11. Pregnancy
- 12. Any other factor that in the investigators judgment may affect patient safety or compliance (e.g. distance greater than 100 miles from procedure site)
- 13. Currently taking psychiatric medications
- 14. Newly initiated psychotherapy (less than 6 weeks)

For patients wishing to discontinue medication: they must agree to work closely with their prescribing physician to wash off medications and the prescribing physician will be their point of contact if side effects or worsening of symptoms occurs.

4.3 Subject Recruitment

All participants will be recruited through the University of Pennsylvania, the Veterans Administration Medical Center, and surrounding community to find 80 patients with PTSD and trauma induced MDD and depressive symptoms. All subjects will express interest by initiating contact with the research staff or by confirming with their referring physician that they wish to be contacted for a screening procedure. All subjects fitting inclusion criteria will be approached by study staff to continue in the study. Additional recruitment methods will include Penn media services, social media, online advertisements (e.g. Craigslist), and fliers to be posted in the local community.

This study will also utilize Facebook as a recruitment resource. The CNDS Lab account will list posts on its page twice a week advertising for this specific study. This account is managed by [name].

In order to facilitate the enrollment of interested subjects in multiple studies, center-wide general prescreening forms phone screen and self-report screen will be used. Because the Center for Neuromodulation in Depression and Stress has numerous studies that are all closely related, in both purpose and eligibility criteria, a general pre-screening (both phone and self-report) has been created. Many participants will be eligible for multiple studies and will be presented the opportunity to participate in all studies that they are eligible for. An additional benefit of a shared or general pre-screening is that participants who do not qualify for a specific study can be informed of other studies they are eligible for. It will be clearly explained to all individuals that this pre-screening is for multiple studies and that their information will be stored in REDCap.

Since approval of v1.0, the center-wide prescreening has successfully increased enrollment of eligible participants across studies as well as significantly reduced burden on interested participants and study staff. The proposed modification (Sept. 2019) to the screening form (v3.4) will update eligibility criteria to be more reflective of current protocols and reduce participant response burden by optimizing branching logic, clarifying language, and implementing standard symptom severity scales. This modification (v3.4) will not be available to potential participants until all actively enrolling CNDS studies obtain IRB approval. Until

that time, potential participants will continue to complete the currently approved version of the general screening form (v1.0).

We will also utilize the Penn Data Store as a recruitment aid. We will ask for a report from the PDS for individuals meeting our basic eligibility criteria, including a diagnosis of post-traumatic stress or adjustment disorder. We will request that the reports contain the following information: patient name, MRN, email, and phone; diagnosing provider & clinic name and date diagnosis was added to problem list. We will not ask for the diagnosis to be listed on this form or for any other PHI. We are only requesting information from outpatient, NON-mental health clinics. As this is a sensitive population, we will be contacting the diagnosing providers for permission to contact their participants who meet our basic criteria. This strategy has been discussed with [name] (Privacy Office), [name] (IRB) and [name] (IRB).

After receiving the list from PDS, we will then message the diagnosing providers via EPIC up to 2 times and attach the patient's record each time. EPIC messaging is a secure way to transmit PHI and all providers we wish to contact will have regular access to EPIC. In order to further protect patient privacy, we will not enter the patient's EMR. The patient's information that is visible when attaching a patient's record to an EPIC message is: Full Name, Age, DOB, Weight, Contact Information, PCP Name, MRN, Penn Medicine Status, and Next Appointment Date.

We will require that providers give expressed approval to contact each patient by indicating either Yes or No next to the patient's name. We will not accept a blanket approval for all of the provider's patients; however, we will accept a blanket request to not contact any of the provider's patients. If providers give us permission to contact their patients, we will contact the patient via email, if provided, with the Patient_Email. If no email is provided, we will call the patients up to 2 times and use the "Penn Data Store – Cure Accelerator Intro" script in the Phone Screen.

Student groups on campus: We may contact the chairs/leaders of student groups on campus who potentially have members that may be able to benefit from this study. We will not request any member information or attempt to contact any members directly; we will email the "StudentGroupEmail" (attached) to the chair of the group from the CNDS email account.

University Student Health and Mental Health Services: We may contact the clinical services on local university campus (including but not limited to Penn). We will send the "StudentServices" email, addressed to the providers at the clinics, requesting them to share the "StudentReferralLetter" with patients who they believe may benefit from this study and additionally requesting that they allow us to leave brochures or flyers within their clinics.

We will also list this study on our laboratory website at https://www.med.upenn.edu/cnds/

4.4 Duration of Study Participation

This study is expected to take place over 22 in-person study visits and 8 phone visits. The approximate amount of time that each study visit will take is outlined in Section 6. In-person visits will all take place over approximately 6-8 weeks. In addition, the study will include a 6-month follow-up period, including 6 telephone and survey visits, with no in-person visits. During the COVID-19 pandemic, visits that can be conducted remotely (screening visit) will be conducted virtually.

4.5 Total Number of Subjects and Sites

It is expected that approximately 80 subjects will be consented/enrolled at Penn in order to produce 40 evaluable subjects in total (due to missing data, drop out, etc.).

4.6 Vulnerable Populations:

No children, pregnant women, fetuses, neonates, or prisoners are included in this research study.

5 Study Intervention (Study drug, device, biologic, vaccine, food etc.)

5.1 Description

Transcranial Magnetic Stimulation (TMS) is a non-invasive form of brain stimulation. TMS can influence activity in various brain regions, and it allows researchers to test or modify brain circuit communication. This study will employ the following investigational devices:

- MagPro X100* magnetic stimulator
- Cool-B65 Butterfly Coil

The MagPro X100* magnetic stimulator and Cool B-65 Butterfly Coil are both approved devices for rTMS treatment of MDD.

5.2 Intervention Regimen

TMS will be administered in theta-burst stimulation (TBS; Huang et al., 2005), which involves triplets of TMS pulses at 50Hz, with intermittent breaks. The intermittent TBS (iTBS) protocol involves 40 trains of 10 TMS triplets, and each train is followed by an 8 second pause. Therefore, each TBS session is administered in a 7-minute block for a total of 1200 stimulations. Subjects then have an approximate 20-minute break before a second 7-minute block of iTBS resumes. Therefore, each stimulation session will involve <3700 stimulations. Stimulation sessions will take place over 10 consecutive weekdays. All subjects will receive iTBS for 10 consecutive weekdays at both target sites as a part of the study. After the first set of 10 stimulation sessions, subjects will have a 3-week break before returning to the laboratory for iTBS administered over an additional 10 consecutive weekdays.

The iTBS in this study will take place at two locations. One site, the DLPFC, is the standard site for TMS treatment. This site is determined by taking scalp measurements and targeting the region 6 cm anterior to motor cortex in a parasagittal line. Targeting for a second site in this study, a sub-region of the DLPFC that we refer to as the fMRI-guided target or LPFC, involves the use of a prior MRI scan to determine the site of stimulation. Structural MRI data will be used to specifically identify the LPFC on each individual's brain. Functional MRI data will further specify the exact location of stimulation, as the precise target for stimulation will be region that demonstrates the greatest activity during functional MRI scanning.

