1.1 Background and Relevant Literature

The subgenual Anterior Cingulate Cortex (sgACC) has been well established as a brain area sensitive to negative mood inductions and implicated in neural abnormalities associated with affective and stress disorders. It is therefore one of the primary targets for deep brain stimulation (DBS) treatment of MDD using surgically implanted DBS devices. Recent posthoc imaging studies of patients who have undergone TMS treatment for depression suggest that treatment outcomes tended to be better when patients were by chance stimulated in an area of lateral prefrontal cortex that had high levels of functional connectivity with sqACC. Based on this finding and on our own interleaved TMS/fMRI probe data, we contend that targeting delivery of TMS to the brain surface non-invasively as indicated by sqACC resting functional connectivity may be especially effective in downregulating sqACC and thereby producing superior clinical outcomes. We have used TMS/fMRI to better understand causal communication among circuits typically examined with resting fMRI alone (Chen et al., 2013). Our recent work suggests that there are specific sites that, when stimulated, influence subcortical brain areas implicated in affective disorders such as the sgACC. Previously, we targeted TMS based on brain atlases mapped onto individual brain surfaces. This proposal will utilize more individualized targeting from participants own resting connectivity data to guide stimulation that we show is especially effective in influencing downstream brain areas of interest. We will focus on a target region that our data suggest is particularly effective at influencing the sqACC. As an alternative brain target, we will also test the efficacy of the dorsolateral prefrontal cortex as a target given its precedence as an FDA-approved stimulation site for remediating depressive symptoms. To increase generalizability to other disorders and to patients with comorbid anxiety and depression (the typical clinical profile), we will recruit patients who are diagnosed with PTSD or trauma induced MDD and who have elevated depression (PHQ). We will recruit them, scan them in the MRI to get anatomical and resting fMRI data to guide TMS, then will invite them to participate in two rounds of two-week TMS treatment to each site (order counterbalanced) with approximately one month between treatments. We will monitor depressive (MADRS), PTSD (PCL Checklist), and quality of life (WHOQOL) measures before, acutely after, and every month for 6 months following TMS treatments to evaluate the effectiveness of each site in mitigating symptoms or improving functioning. A typical, FDA-approved clinical application of TMS involves long trains of repetitive TMS applied for approximately 40 minutes, 5 days/week, over 2-6 weeks, for a total of 10-30 TMS visits. The present study utilizes the same FDA-approved devices (Magventure Cool-Coil B65, MagVenture X100 Stimulator) to administer treatment. We will be modifying the FDA-approved protocol to stimulate similarly to a well-replicated protocol, theta-burst stimulation (Huang et al., 2005). We have attached several additional examples of prior studies which have safely utilized TMS outside of its FDAapproved protocol, even in heightened doses. For instance, in prior studies subjects have received FDAapproved 3000 rTMS pulses, but done bilaterally instead of unilaterally (6000 total stimulations) every weekday over 4-6 weeks (see Bakker et al., 2015). Similarly, subjects have received 3600 rTMS pulses every weekday over 10 days (see Chistyakov et al., 2015), or 3000 rTMS pulses every weekday over 6 weeks (see O'Reardon et al., 2007). Another study applied the FDA-approved protocol in more than a double-dose, with 6800 stimulations to 1 site every weekday over 7 weeks average participation (Hadley et al., 2013). The present study utilizes fewer stimulations than the FDA-approved protocol, with each visit including a maximum of 3700 pulses. For additional information, please see Anderson et al., 2006 for demonstrations of the safety of repeated exposure to TMS. Likewise, please see Wagner et al., 2007 and Parkin et al., 2015 for reviews of the importance of TMS research and how our proposed studies fit in the present and growing body of literature.

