1.3 Dose Rationale

Several prior studies have safely utilized TMS outside of its FDA-approved protocol, even in substantially larger doses. For instance, in prior studies subjects have received the FDA-approved 3000 rTMS pulses, but done bilaterally instead of unilaterally (6000 total stimulations) every weekday over 4-6 weeks (see Bakker et al., 2015). Similarly, subjects have received 3600 rTMS pulses every weekday over 10 days (see Chistyakov et al., 2015), or 3000 rTMS pulses every weekday over 6 weeks (see O'Reardon et al., 2007). Another study applied the FDA-approved protocol in more than a double-dose, with 6800 stimulations to 1 site every weekday over 7 weeks average participation (Hadley et al., 2013). The present study utilizes many fewer stimulations than these recent/established protocols, with each visit including a maximum of 3700 pulses (including motor threshold determination).

2 Study Objectives

We aim to establish the clinical efficacy of TMS stimulation using targets defined by resting connectivity in patients. We hypothesize that MRI-defined TMS will yield greater reductions in symptoms and greater improvements in quality of life among patients. In addition, we hypothesize that greater resting state connectivity will predict greater reductions in symptoms following TMS.

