3.2 Study Endpoints

3.2.1 Primary Study Endpoints

The primary endpoint will be clinical improvement due to TMS at either of the two target regions. The study will focus on a target region of the fMRI-guided target and the standard DLPFC target, which is an FDA-approved rTMS treatment site. TMS-induced changes in brain activity are likely different for these two stimulation sites, despite their proximity. The aim of this study is to establish if using targets defined by resting connectivity in patients can be more effective at treating MDD/PTSD compared with standard targets.

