3.2.2 Secondary Study Endpoints

The secondary endpoint to be analyzed in this study will be the relationship between baseline fMRI activity and the clinical improvement over the course of the study in the MDD/PTSD patients.

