6.2 Study Intervention Phase

6.2.1 Visit 1 (sometimes referred to as the baseline visit)

Visit 1 (aka Baseline) will take approximately 2-3 hours. If participants have time limitations, we may provide the option to complete the clinical assessments remotely (by phone/ sending the surveys) or to split the visit in two visits. If any of these adjustments are made, we will make a note in their records. At the first study session, subjects will complete 60 minutes of structural MRI and resting-state fMRI scans. Structural and functional scans will be obtained in each session on a clinically-approved 3 Tesla Siemens Prisma (Erlangen, Germany) scanner, equipped with 40mT/m gradients and 200 mT/m/s slew-rates. RF transmission will use a quadrature body-coil, and reception will use a Siemens receive-only 64-channel head coil. The total time in the scanner will be approximately 60 minutes. An experienced technician and a member of the study team will be present during the MR session to ensure participant safety and well-being.

Additionally, clinical assessments of thoughts, mood, and behaviors will be completed. Subjects will complete the following neurocognitive assessments during this visit:

- i. Nback task: Computerized task to measure working memory capacity.
- ii. Trails A & B task: Computerized task of visual attention and task switching.
- iii. Stroop/Word task: Neurophysiological testing of cognitive interference.
- iv. Foraging task: Computerized test to measure reward seeking behaviors.

In collaboration with [name] from the [name] Lab, EEG data will be collected when the participants are engaged in the above-mentioned tasks. We may also record the location of their gaze at any particular time during these tasks using a passive eye-tracking device. The eyetracker will use a camera to identify the position of the pupil and cornea (using near-infrared reflection). By tracking the gaze of the subjects as they make decisions, we can obtain information about what subjects attended to during their decisions, for how long they attended to it, and in what order they attended to it.

6.2.2 Visits 2 - 11

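### Section 5.2 picks the fMRI-guided site by greatest activity, while the aim and rationale define it by resting connectivity

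*Combined protocol and SAP*

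**What the plan says.** Section 5.2 describes two sites. The standard DLPFC site comes from scalp measurement. For the fMRI-guided site, structural MRI locates the LPFC and functional MRI then fixes the point within it: "the precise target for stimulation will be region that demonstrates the greatest activity during functional MRI scanning". The description of that target in 5.2 mentions neither connectivity nor sgACC.

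The rationale and aims describe the same target differently:

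- Section 1.1: "This proposal will utilize more individualized targeting from participants own resting connectivity data to guide stimulation". The argument there is for "targeting delivery of TMS to the brain surface non-invasively as indicated by sqACC resting functional connectivity".
- Section 2: "We aim to establish the clinical efficacy of TMS stimulation using targets defined by resting connectivity in patients".
- Section 3.2.1 gives the study aim as finding out "if using targets defined by resting connectivity in patients can be more effective at treating MDD/PTSD compared with standard targets".

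On the scan itself, section 6.2.1 says "subjects will complete 60 minutes of structural MRI and resting-state fMRI scans".

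The baseline imaging predictor is also described in two ways. Section 3.2.2 makes the secondary endpoint "the relationship between baseline fMRI activity and the clinical improvement over the course of the study". The hypothesis in section 2 reads "we hypothesize that greater resting state connectivity will predict greater reductions in symptoms following TMS", and both 2.2 and 7.2 correlate pre-TMS resting-state connectivity with clinical change. Section 7.5, giving an example of how incomplete participants' data may be used, again refers to fMRI activity.

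**The concern.** The way the site is chosen is what separates the experimental condition from the standard one. Regional activity belongs to one location; connectivity with sgACC is a relationship between two. The location with the highest value of one need not have the highest value of the other.

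The comparison of standard with fMRI-guided stimulation in 2.1 would go ahead under either rule. Its interpretation would not be the same. A result obtained with activity-chosen sites says nothing direct about whether connectivity-defined targets work better, which is the question in sections 2 and 3.2.1.

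The secondary endpoint has a smaller version of the same problem. With one predictor in 3.2.2 and another in 7.2, the plan leaves room to settle which one was meant after the data are seen.

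**Working it through.** No power, error-rate or sample-size figure is involved, so the check is a comparison of sections.

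**1. How the fMRI-guided target is defined**

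| Section | Role | Basis for the target |
|---|---|---|
| 1.1 | Rationale | Individual resting connectivity, with sgACC |
| 2 | Aim | Resting connectivity |
| 3.2.1 | Aim under the primary endpoint | Resting connectivity |
| 1.2.1.1 | Clinical background | Participants' own fMRI scans (fits either rule) |
| 5.2 | Operating rule | Greatest activity |

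Three sections say connectivity, one says activity and one is neutral. The one that says activity is the one that tells staff how to choose the site. No section reconciles the two.

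**2. Whether the planned scan fits an activity rule**

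Section 6.2.1 lists structural and resting-state acquisition and describes no task in the scanner. The neurocognitive tasks at that visit are paired with EEG and eye tracking, not with fMRI. No activation contrast is therefore defined from which a region of greatest activity could be read. A regional measure could be computed from resting data, but the plan names none. The scan fits the connectivity definition. Section 12.3 also allows an MRI from another study at the center to be reused without saying what it must contain, which is a further reason to name the measure.

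**3. How the secondary predictor is defined**

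| Section | Predictor |
|---|---|
| 2 | Resting-state connectivity |
| 2.2 | Resting-state connectivity |
| 7.2 | Resting-state connectivity |
| 3.2.2 | Baseline fMRI activity |

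Here too the split is three to one. Section 7.5 uses the activity label as well but defines neither a target nor a predictor. The label therefore appears in three sections in all: 3.2.2, 5.2 and 7.5.

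**4. Scope of the 5.2 sentence**

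Section 3.1 gives 10 sessions per site and 20 per participant; section 4.5 gives 40 evaluable participants.

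- Sessions at the fMRI-guided site: 40 × 10 = 400.
- All TMS sessions: 40 × 20 = 800.
- Share: 400 / 800 = one half.

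This is the share of treatment the sentence governs. It does not estimate how many sessions were aimed at the wrong place.

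**The case against.** The best answer is that this is loose wording and the intent is plain. Sections 1.1, 2 and 3.2.1 all point to connectivity, only resting-state functional data are planned, and activity may be shorthand for whatever the resting scan shows. The label recurs in 3.2.2 and 7.5, which supports that reading. Nothing in the documents shows a site chosen by an activity rule, so any harm depends on staff following 5.2 to the letter. This is fair, and it is why the consequence is stated conditionally. It does not remove the problem: someone generating or replicating targets would turn to 5.2, and background text does not replace the operating rule.

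Three narrower points also carry weight. The session count is simply half of a two-site crossover and does not measure impact. The 7.5 wording is a descriptive example and conflicts with nothing by itself. For the secondary endpoint, 7.2 sits in the statistical plan and states the correlation to be analysed, so the conflict with 3.2.2 matters less than the one in 5.2.

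Finally, sgACC is tied to the target only in the rationale, and no section gives a sign or peak criterion, so a corrected rule needs choices the documents do not contain. That is true. It means the amendment must record a scientific decision as well as change a word; it does not justify leaving the activity rule in place.

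**Conclusion.** The point holds and should be fixed. Section 5.2 states a different targeting rule from the one the aim requires, and it is the only operating rule for the experimental site. Section 3.2.2 likewise names a different predictor from 2.2 and 7.2.

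The mismatch in the text is certain. Its practical effect is unknown: the documents give no basis for saying how far apart the two rules would place the coil, or what that would do to symptom scores. The conclusion assumes only that activity and connectivity carry their ordinary, distinct meanings. If the team already uses sgACC connectivity, the written intervention is wrong but the delivered one is not, and the amendment simply brings the text into line.

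**What to change.** Replace the last sentence of 5.2 with a rule along these lines: within the LPFC identified on structural MRI, the target is the site with the strongest resting-state functional connectivity to sgACC in the participant's own scan. State the sgACC seed, the LPFC search region, whether strongest means most positive or most negative, and how the peak is picked. Fix all of these before targets are generated.

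In 3.2.2, replace fMRI activity with pre-TMS resting-state connectivity so that it matches 2.2 and 7.2. Make the same change in 7.5 for consistency; the 5.2 correction stands without it.

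The cost is a short amendment to three sections, plus the team's decision on seed, sign and peak, which is needed to generate a connectivity target at all. It adds no scans, visits or participants.
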